9.3.2. Indication

Indication will be estimated from the diagnoses recorded in the time period preceding each domperidone prescription:

- The indication for the prescription will be defined as nausea/vomiting if the subject has a recorded diagnosis classified as nausea or as vomiting, on the day of the prescription or in the preceding 7 days.
- For those prescriptions whose indication is not defined as nausea/vomiting, the indication will be defined as off-label if the subject has, in the 2 months up to and

including the date of domperidone prescription, a diagnosis classified as one of the following:

- o GERD;
- Abdominal bloating, gastric dysmotility, delayed gastric emptying;
- o IBS;
- Suppressed lactation, failed lactation, lactation not established, decreased lactation, lactation problem; or
- Orthostatic hypotension and a diagnosis of Parkinson's disease.
- For those prescriptions not classified as above, the indication will be classified as unknown.

For a list of the diagnostic terms and codes that will be used to identify the above conditions, see Annex 6.

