9.3.4. Use in Patients with Contraindicated Conditions

The contraindication for moderate or severe hepatic impairment will be identified by any diagnosis of hepatic cirrhosis, hepatic failure, or hepatic coma, between 1 January 2011 and 1 day before the prescription was written. The cardiac contraindication will be identified by a diagnosis of QTc prolongation, ventricular arrhythmia, or congestive heart failure in the 6 months before the prescription was written, or a diagnosis of hypokalemia in the 30 days before the prescription was written.

9.3.5. Concurrent Use with Drugs that Prolong the QT Interval or are Potent CYP3A4 Inhibitors

Domperidone is used as needed, therefore the duration of use may not be the same as the number of days for which domperidone is supplied. As a result, duration of use will be assessed under the following 2 scenarios, which will be likely to bracket the actual (but unknown) situation:

- 1. Domperidone is used only for as little as 1 dose after it is prescribed, and
- 2. Domperidone is used for the entire number of days supplied.

For the first scenario, the assessment of concurrent use with contraindicated medications will focus on drugs that were prescribed before or on the date of the domperidone prescription and whose duration of use includes the date of the domperidone prescription. For the second

scenario, assessment of concurrent use with contraindicated medications will also include drugs that were prescribed during the days' supply of the domperidone prescription.

A list of drugs that are known to prolong the QT interval is provided in Annex 3 and those that are potent or strong CYP3A4 inhibitors appear in Annex 4.

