9.3.6. A Composite Endpoint -All Label Requirements

Each prescription will be classified according to whether it appears to violate at least 1 of the above specifications, i.e., has a presumed indication that is off-label, has a dose that is above 30 mg/day (for ages \geq 12 years) or above 0.75 mg/kg/day (for ages <12 years), is written for a patient with a contraindicated condition, or appears to be prescribed concurrently with a medication contraindicated for concurrent use.

To accommodate the 2 areas of uncertainty described above (1] duration of domperidone use and 2] domperidone prescriptions for which the indication is unknown), the above classification will be done in the following 4 ways to reflect the possible combinations of:

- With consideration of days' supply being more than 7 days;
- Without consideration of days' supply being more than 7 days;
- With classifying subjects with an unknown indication as having an off-label indication; and
- Without classifying subjects with an unknown indication as having an off-label indication

This is described in more detail in Section 9.7.

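### Section 9.3.4 leaves the prescription day out of the hepatic contraindication window, and by plain reading out of the cardiac and hypokalaemia windows, although indication and co-medication count that day

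*Protocol*

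**What the plan says.** Section 9.3.4 sets three look-back windows for contraindicated conditions:

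- Hepatic (cirrhosis, failure or coma): any diagnosis from 1 January 2011 to "1 day before the prescription was written".
- Cardiac (QTc prolongation, ventricular arrhythmia, heart failure): the last item reads "congestive heart failure in the 6 months before the prescription was written".
- Hypokalaemia: "a diagnosis of hypokalemia in the 30 days before the prescription was written".

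The neighbouring definitions treat the day differently. In Section 9.3.2 a nausea or vomiting diagnosis counts if recorded "on the day of the prescription or in the preceding 7 days". The off-label window is two months up to and "including the date of domperidone prescription, a diagnosis classified as one of the following". In Section 9.3.5 the first scenario for co-medication covers "drugs that were prescribed before or on the date of the domperidone prescription".

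Under Section 9.3.6 a prescription fails the composite if it "is written for a patient with a contraindicated condition". Section 9.7 carries this condition into all four versions of the composite without giving another window, so Section 9.3.4 governs each of them. The protocol gives no reason for the different day rule and plans no sensitivity analysis on it.

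**The concern.** Section 9.4 and Annex 5 describe sources built largely from records of office visits, where diagnoses and prescriptions can be entered together. The protocol relies on this: Section 9.9.2 explains that indication is inferred from diagnoses recorded on the prescription day or shortly before. A contraindication coded at that same visit is closely tied to the prescribing decision, yet under the hepatic rule it cannot make the prescription non-compliant.

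Two results are exposed. One is the proportion of prescriptions written for patients with a contraindicated condition, a secondary estimate under Section 8.2. The other is the level of compliance on the primary composite. Section 9.9.2 already accepts that some contraindicating diagnoses are lost because patients see several physicians. That loss cannot be avoided with these data; this one can.

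**Working it through.** The protocol states no figure on this point, so there is none to reproduce. The check compares the windows and then gives an illustration.

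**Is the prescription day counted?**

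- Nausea/vomiting (9.3.2): yes, stated.
- Off-label indication (9.3.2): yes, stated.
- Contraindicated co-medication (9.3.5): yes, stated, in both scenarios, because the second adds to the first.
- Hepatic (9.3.4): no, stated.
- Cardiac (9.3.4): not stated; excluded on a plain reading of before.
- Hypokalaemia (9.3.4): not stated; the same reading.

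**Which prescriptions are misclassified?** For the contraindication component, those whose only code within the window falls on the prescription day. For the composite, only those among them with no other violation, since any other violation already makes the prescription non-compliant.

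**Assumed size.** The documents give no frequency. Suppose 2% to 5% of prescriptions go to patients with a contraindicated condition, and 10% to 20% of these carry the code only on that day:

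- low: 0.02 × 0.10 = 0.002, or 0.2 points of all prescriptions;
- high: 0.05 × 0.20 = 0.010, or 1.0 point.

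By the same assumption the component itself is understated by 10% to 20% in relative terms. For the composite, 0.2 to 1.0 points is an upper range, because some of these prescriptions fail for another reason.

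**Effect on the risk ratio.** Take the ratio as post over pre, as in Section 9.5. Let c0 be true pre-period compliance, c1 = 1.10 × c0, and s0 and s1 the shares wrongly scored compliant. Then observed ratio = (c1 + s1) / (c0 + s0).

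Equal shares, c0 = 10%:
- s = 0.2 points: 0.112 / 0.102 = 1.098
- s = 1.0 point: 0.120 / 0.110 = 1.091
- s = 2.0 points (wider assumption): 0.130 / 0.120 = 1.083

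Equal shares, c0 = 50%:
- s = 0.2 points: 0.552 / 0.502 = 1.0996
- s = 1.0 point: 0.560 / 0.510 = 1.098
- s = 2.0 points: 0.570 / 0.520 = 1.096

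Unequal shares, to show what a large shift would require:
- c0 = 10%, 2 points pre and 1 point post: 0.120 / 0.120 = 1.00; reversed: 0.130 / 0.110 = 1.18
- c0 = 50%, 2 points pre and 1 point post: 0.560 / 0.520 = 1.08; reversed: 0.570 / 0.510 = 1.12

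These last cases need the share to halve or double between periods. Nothing in the protocol supports such a change.

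**The case against.** Several arguments on the other side have force.

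- **The exclusion is explicit only for hepatic disease.** Section 9.3.2 introduces windows that include the prescription day as a period preceding the prescription, so before in Section 9.3.4 need not exclude it. This stands. For the cardiac and hypokalaemia windows the defect is an ambiguity, which a programming specification could settle either way. It does not help the hepatic rule.
- **Most affected patients will have an earlier code.** The hepatic search runs back to 1 January 2011, and a condition coded at one visit is caught at later prescriptions within the window. This stands and limits the size.
- **The order of events may be reversed.** Section 7.2 lists QT prolongation and arrhythmias as adverse effects of domperidone, and Section 9.3.1 lets laboratory results determine diagnoses. A same-day cardiac code may follow the prescription, and a same-day potassium result may not have been available to the prescriber. This is a real drawback of counting the day for those two windows. It has little force for long-standing liver disease, and the protocol accepts the same uncertainty for indication. A sensitivity analysis can measure it.

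A reader might also infer two stronger claims that the protocol does not support. The first is that the loss falls mainly on patients new to the practice. Section 9.2.1 requires at least 180 days of history before the prescription, so such patients are not in the cohort. The second is that the error makes the label change look more effective. It raises compliance levels, but the primary statistic is a ratio between periods, and equal shares in both pull that ratio toward 1.

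**Conclusion.** The point holds as a minor one. The prescription day is expressly excluded for hepatic contraindications and left unstated for cardiac disease and hypokalaemia, against the protocol's own rule for indication and co-medication and without a reason. Followed as written, a hepatic contraindication first coded at the prescribing visit passes as compliant in every version of the composite and is absent from the contraindication component. On the plain reading, the same applies to a cardiac or hypokalaemia diagnosis with no earlier code in its window.

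The direction is certain for levels only: contraindicated prescribing can only be understated and compliance only overstated. The size rests wholly on assumed frequencies. With 0.2 to 1.0 points affected equally in both periods, a true ratio of 1.10 moves to between 1.091 and 1.0996 over baseline compliance of 10% to 50%, which would not change a conclusion about effectiveness. The relative effect on the contraindication component could be larger, and that is the main reason to correct the rule.

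**What to change.** Reword the three windows in Section 9.3.4 (hepatic, cardiac, hypokalaemia) so that each runs through the prescription date, in line with Sections 9.3.2 and 9.3.5. Report a sensitivity analysis that leaves the prescription day out, for the contraindication component and for the four composite risk ratios.

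The cost is a few words in the protocol and one additional flag in a retrospective query; no new data are needed. The drawback is that a few same-day cardiac diagnoses or potassium results that came after the prescription would be counted as violations. The sensitivity analysis shows how much the day matters in total, and so bounds that error.

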4. ABSTRACT

Title of Study

A Drug Utilisation Study of Domperidone in Europe Using Databases

Rationale and Background

In March 2013, the European Medicines Agency (EMA) Pharmacovigilance Risk Assessment Committee (PRAC) initiated a review of domperidone-containing medicines at the request of the Federal Agency for Medicines and Health Products (FAMHP), under Article 31 of Directive 2001/83/EC over concerns about cardiac adverse effects of domperidone. Subsequently, PRAC recommended that the product label (Summary of Product Characteristics/SmPC and Patient Information Leaflet/PIL) of domperidone-containing medicines be updated to strengthen the information regarding cardiac risks. In addition, PRAC raised concerns that there may be off-label use of domperidone for the stimulation of lactation in breastfeeding women, for the treatment of gastro-oesophageal reflux disease (GERD), for the treatment of diabetic and non-diabetic gastroparesis, and for the treatment of symptoms of postural hypotension in Parkinson's patients. More recently the EMA asked that inflammatory bowel syndrome (IBS) be included in the present study as an off-label indication.

The recommended changes following conclusion of the Article 31 referral included the following:

- restriction of the indication to nausea and vomiting;
- limitation of duration of use to 7 days;
- reduction of the maximum daily dose to 10 mg TID for adults and adolescents (12 years of age and older and weighing 35 kg or more);
- reduction of the maximum daily dose to 0.25 mg/kg TID for neonates, infants, children (less than 12 years of age), and adolescents weighing less than 35 kg;
- contraindication of the combination with other drugs that increase the cardiac risks by themselves or increase the plasma level of domperidone; and
- contraindication in patients with moderate or severe hepatic impairment or certain cardiac conditions.

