9.2. Setting and Study Population

9.2.1. Study Setting and Population

The study population will be defined as all patients receiving domperidone in the outpatient setting during the pre-defined periods (pre- and post- implementation periods of the risk minimisation activity) in the selected European Union countries (France, Germany, United Kingdom, Belgium, and Spain). Patients will be included in the study cohort if they have at least 1 prescription for domperidone in the selected databases during the pre-defined periods, and have membership or have been registered with the practice and have available medical history for at least 180 days before the domperidone prescription.

The date of the first prescription of domperidone in the pre-defined study periods will be defined as the index date. Patients will be followed from the index date to the earliest of the following dates:

- end of the study period;
- transfer out of the practice; or
- end of the practice's qualification as up to standard (a designation used in some databases to differentiate between practices that meet a data standard and those who do not for databases, such as CPRD).

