9.2.2. Study Period

The study period will be divided into a background period and pre- and post- implementation periods of risk minimisation measures as follows:

- A background period (1 January 2011 through 31 March 2013)
- A 1-year pre-implementation period of risk minimisation measures (1 April 2013 through 31 March 2014)
- A 1-year post-implementation period of risk minimisation measures (1 October 2014 through 30 September 2015)

The period during which the label change took place and the DHPC was sent will be used as the period during which the risk minimisation measures were implemented (1 April 2014 through 30 September 2014).

Because the amendments to the product information were suggested by the PhVWP in October 2011, the study will track prescribing pattern changes from 1 January 2011 (a time that preceded most of the discussion and implementation of the label changes, i.e., a background period) through 30 September 2015.

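### Heart failure counts as a contraindication only if coded in the previous 6 months, so contraindicated cardiac use is likely understated in all four composite versions

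*Protocol*

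**What the plan says.** Protocol Section 9.3.4 sets different look-backs within one paragraph. The hepatic contraindication is "any diagnosis of hepatic cirrhosis, hepatic failure, or hepatic coma", searched "between 1 January 2011 and 1 day before the prescription was written". The cardiac contraindication is QTc prolongation, ventricular arrhythmia or "congestive heart failure in the 6 months before the prescription was written", or hypokalaemia in the preceding 30 days. No reason is given for the different windows.

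The restriction being measured is given in the Abstract and in Section 7.2 as a "contraindication in patients with moderate or severe hepatic impairment or certain cardiac conditions", with no recency limit. Section 9.3.6 counts a violation when a prescription "is written for a patient with a contraindicated condition". In Section 9.7 all four composite versions contain the same item on cardiac and hepatic conditions; they differ only in how they treat unknown indication and days' supply. Section 8.2 makes each component a secondary objective, and Section 9.7 compares each component between the two periods.

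**The concern.** Heart failure, like cirrhosis, is ordinarily a persisting condition. A patient with heart failure coded 8 months before the prescription and not since is still a patient with the condition, yet passes the cardiac item. The error runs one way: it can hide violations but cannot create them.

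The four composite versions are meant to span the plausible range of compliance. Because none varies the cardiac look-back, even the version labelled most pessimistic carries this optimistic element. Section 9.9.2 accepts that some contraindicating diagnoses will be missed, but only because patients may attend several physicians; it does not mention the window. Cardiac risk prompted the label change, so the cardiac component is one that readers will look at in its own right.

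**Working it through.** The protocol states no figure that depends on this definition, so there is none to reproduce. The check is date arithmetic plus a simple misclassification calculation.

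**Calendar look-backs (dates from Sections 9.2.2 and 9.3.4)**

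- Heart failure: 6 months before every prescription, in both periods.
- Hepatic, pre-period: 1 January 2011 to 1 April 2013 is 27 months; to 31 March 2014 it is about 39 months.
- Hepatic, post-period: 1 January 2011 to 1 October 2014 is 45 months; to 30 September 2015 it is about 57 months.
- The hepatic window is therefore 27/6 = 4.5 to 57/6 = 9.5 times as long as the cardiac one, and 45 − 27 = 18 months longer in the post-period than in the pre-period.

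These are calendar maxima. A patient need only "have available medical history for at least 180 days before the domperidone prescription", so actual history may be much shorter.

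**Size of the undercount (inputs assumed; none is in the documents)**

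- h = share of prescriptions written for patients with heart failure, 1% to 5%.
- s = share of those with a heart-failure code in the prior 6 months, 30% to 80%.
- q = share of prescriptions compliant on everything else, 50%, taken as independent of heart failure.

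Heart-failure violations found = s·h. Missed = h(1 − s). True composite compliance = q(1 − h); observed = q(1 − s·h); overstatement = q·h(1 − s).

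| h | s | found | missed | composite overstated by |
|---|---|---|---|---|
| 1% | 80% | 0.8% | 0.2% | 0.10 points |
| 3% | 50% | 1.5% | 1.5% | 0.75 points |
| 5% | 30% | 1.5% | 3.5% | 1.75 points |

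**Effect on the risk ratio** (post divided by pre, the direction in which Section 9.5 reads an improvement)

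- h and s equal in both periods: the factor (1 − s·h) cancels and the ratio is unchanged.
- h halves after the label change: the true contribution is (1 − h/2)/(1 − h), and the observed one is (1 − s·h/2)/(1 − s·h). For h = 1% the true value is 0.995/0.99 = 1.005, against an observed 0.9985/0.997 = 1.0015 when s = 30%. For h = 5% the true value is 0.975/0.95 = 1.026, against an observed 0.98/0.96 = 1.021 when s = 80%. The improvement is understated, but slightly.
- h = 3% and s rises from 40% to 60% with no change in prescribing: the heart-failure count goes from 1.2% to 1.8%, and the composite ratio is 0.982/0.988 = 0.994.

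**What copying the hepatic rule would do.** If the longer post-period window raised capture from 70% to 80% with h constant, the artefactual ratio would be 0.992/0.993 = 0.999 for h = 1% and 0.960/0.965 = 0.995 for h = 5%. This is small, but it works against improvement.

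**The case against.** The strongest defence is that a 6-month window has the same length in both periods and nearly matches the 180 days of history that eligibility guarantees. For a within-country pre/post ratio, equal ascertainment is a reasonable aim, and on that criterion the hepatic rule is the weaker of the two. This stands as a reason to keep the 6-month version and not to copy the hepatic rule. It does not make the 6-month count an adequate measure of the level of contraindicated use, and the protocol does not offer it as the reason.

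It can also be said that the IMS databases may carry standing conditions forward. Annex 5 lists comorbidities as well as diagnoses for all four, and does not say how they are dated. If they are re-dated at each visit, s is close to 100% and the problem shrinks. That is unknown, and reporting a longer window alongside would settle it.

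A reader might infer more than the text supports:

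- *That all patients with established heart failure are scored compliant.* Only those without a code in the prior 6 months pass this item, and their prescriptions count as compliant only if every other component passes.
- *That every patient has at least 27 months of hepatic search.* The 180-day rule means some have about 6 months.
- *That the safety communication would prompt re-coding, so that the cardiac component appears to worsen by half.* The move from 1.2% to 1.8% follows from assumed figures; nothing in the documents shows that re-coding would change, and the composite ratio would move by only 0.6%.
- *That the protocol contradicts itself.* It does not: differing windows are a stated operational choice, left unexplained.

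**Conclusion.** The point holds for levels. As defined, the cardiac component is likely to understate contraindicated prescribing, and all four composite versions are likely to overstate compliance, because standing heart failure without a recent code is invisible to them. The size cannot be found from the documents. Under the assumed ranges it is 0.2% to 3.5% of prescriptions missed on this item and 0.1 to 1.75 percentage points on the composite, with 50% compliance otherwise and independence between components.

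It would be wrong to conclude that the primary comparison is invalid. The risk ratio is unchanged if prevalence and coding are stable, and moves by about 2% or less in the scenarios worked above. Section 9.5 treats improvements below 10% as of limited public health interest. The change is worth making for the component the study reports and compares, and for the absolute compliance figures.

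**What to change.** In Section 9.3.4, for the two comparison periods, also identify congestive heart failure with a longer look-back of the same fixed length before every prescription in both periods. Leave the windows for the other cardiac items as they are.

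- **Length.** Set it to what each database supports. The primary ratio is calculated within country, so the length may differ between countries but not between periods. Any length up to 27 months stays within the calendar span from 1 January 2011 that the hepatic search already uses. Annex 5 dates Spanish specialist collection from 2012, so a prescription on 1 April 2013 has at most 15 months of it; 27 months is not available there.
- **Reporting.** Give the longer-window result beside the 6-month result for the cardiac component and the composite, with a check restricted to patients who have that full length of history.
- **Do not extend the hepatic rule to heart failure.** Its calendar look-back grows by about 18 months between the periods.
- **Background trend.** For 2011 to early 2013, keep the 6-month window where earlier data do not exist; otherwise a lengthening look-back would itself create a trend.
- **Limitation.** State in Section 9.9.2 that the 6-month window can miss standing heart failure.

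The cost is protocol wording, one added look-back parameter and extra table columns, with no new data source. The downside is that fewer patients have the full history and some old codes may be provisional; showing both versions makes the effect visible.
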